6.0 Investigator, Sponsor, and IRB/EC Responsibilities**6.1 Investigator's Responsibilities**

The Investigator will comply with Good Clinical Practices (GCPs) and applicable regulatory requirements, as itemized below.

- The Investigator shall be familiar with the appropriate use of The Volara® System and any other information provided by the Sponsor.
- The Investigator shall provide adequate staff to conduct and complete the study within the agreed study time period. The Investigator shall ensure that all persons assisting with the study are adequately informed about the protocol, The Volara® System and their study related duties.
- A qualified physician delegated as the Investigator will be responsible for all study related duties and functions. During a subject's participation, the

PROTOCOL TITLE**Evaluation of Oscillation and Lung Expansion (OLE) using The Volara® System for treatment of respiratory complications in patients with neuromuscular disease in the home setting****Final Protocol****Protocol Number:** CR-RR-2020-005**Date:** 11May2022

Investigator/Institution shall ensure that adequate medical care is provided to the patient for any adverse event.

- The Investigator shall have written and dated approval from the IRB/EC for the protocol, informed consent and assent forms or waiver of informed consent, HIPAA authorization, patient recruitment procedures and any other written information for the conduct of the study and/or to be provided to patients.
- The Investigator/Institution shall conduct the study in compliance with the protocol agreed to by the Sponsor. The Investigator shall sign the protocol or alternative contract to confirm agreement. The Investigator shall not implement any deviation or changes to the protocol without agreement with the Sponsor and prior review and agreement from the IRB/EC, unless the deviation or change is to eliminate an immediate hazard to study patients.
- The Investigator/Institution shall maintain subject confidentiality.
- In obtaining and documenting informed consent (and assent if minor subject), the Investigator must comply with the applicable regulatory requirements and shall adhere to GCP and the ethical principles that have their origin in the Declaration of Helsinki.
- The Investigator, per Title 21 Code of Federal Regulations Part 54, shall disclose any financial interests that could affect the reliability of the data.
- The Investigator shall ensure the accuracy, completeness, legibility and timeliness of the data reported to the Sponsor in the CRFs and required reports.
- The Investigator shall maintain the study documents as required by the applicable regulatory requirements. Records must be maintained for a period of three years after the latter of the following dates: the date the study is completed/terminated or the date of the last regulatory approval based on the study data. The

PROTOCOL TITLE**Evaluation of Oscillation and Lung Expansion (OLE) using The Volara® System for treatment of respiratory complications in patients with neuromuscular disease in the home setting****Final Protocol****Protocol Number:** CR-RR-2020-005**Date:** 11May2022

Investigator or Institution shall notify the Sponsor at least thirty (30) days prior to any planned destruction of records from this study.

- The Investigator shall submit written summaries of the status of the study to the IRB/EC annually, or as requested by the IRB/EC, and upon completion of the Study.
- All serious adverse device effects (SADE) and unanticipated adverse device effects (UADE) shall be reported immediately to the Sponsor and per the local IRB/EC's reporting policy at that site. The initial reports shall be followed by more detailed reports if more information becomes available. If the study is terminated prematurely or suspended for any reason, the Investigator shall promptly inform the study patients and ensure appropriate therapy and follow-up is scheduled or documented for each patient.

6.2 Sponsor's Responsibilities

The Sponsor of the program is Hillrom Company, Inc. The Sponsor's, responsibilities are itemized below.

- The Sponsor is responsible for implementing and maintaining quality assurance and quality control systems with written standard operating procedures (SOPs) to ensure that studies are conducted and that the data are generated, documented, and reported in compliance with the protocol, GCPs and applicable regulatory requirements. The Sponsor is responsible for securing an agreement from all involved parties to ensure direct access to all study-related sites, source documents, and reports for the purpose of monitoring and auditing.
- The Sponsor may transfer any or all of the study-related duties and functions to a Contract Research Organization (CRO), but the ultimate responsibility for the quality and integrity of the data resides with the Sponsor.

PROTOCOL TITLE

Evaluation of Oscillation and Lung Expansion (OLE) using The Volara® System for treatment of respiratory complications in patients with neuromuscular disease in the home setting

Final Protocol

Protocol Number: CR-RR-2020-005

Date: 11May2022

- The Sponsor shall use an unambiguous patient identification code that allows for de-identification of all the data reported for each patient.
- The Sponsor shall retain the essential documents as required by the applicable regulatory requirements. Records must be maintained for a period of three years after the latter of the following dates: the date the study is completed/terminated or the date of the last regulatory approval.
- The Sponsor shall ensure the Investigator(s) selected for the study have the proper qualifications, training, and resources to perform the study adequately.
- The Sponsor shall provide the Investigator(s) with a protocol and an Investigator Brochure (or equivalent documentation) and allow sufficient time for the Investigator to review the information provided.
- The Sponsor shall ensure timely delivery of the Device(s); maintain records that document shipment, receipt, disposition, return and destruction (if applicable) of the Devices; maintain a system for retrieving Devices and documenting this retrieval; maintain a system for the disposition of unused Device(s) and for the documentation of this disposition.
- The Sponsor shall ensure that it is specified in the protocol or other written agreement that the Investigator(s)/Institution(s) provide direct access to source documents for study-related monitoring, audits, IRB/EC review, and regulatory inspection. The Sponsor shall verify that each patient has consented in writing, to direct access to his/her original medical records for study-related monitoring, audit, IRB/EC review and regulatory inspection, or that informed consent has been waived.
- The Sponsor is responsible for submitting reports of all recalls and device disposition to the IRB/EC and the FDA, as applicable.

PROTOCOL TITLE

Evaluation of Oscillation and Lung Expansion (OLE) using The Volara® System for treatment of respiratory complications in patients with neuromuscular disease in the home setting

Final Protocol

Protocol Number: CR-RR-2020-005

Date: 11May2022

6.3 Institutional Review Board (21 CFR Part 56) / Ethics Committee

- Prior to study initiation, the appropriate IRB/EC must review and give written approval for the study and provide the approved informed consent form. It is the responsibility of the Investigators, in collaboration with the Sponsor, to provide the IRB/EC with all necessary information to satisfy the individual Institution's requirements.
- Informed consent must be obtained from all subjects, or legally authorized representative, prior to participation as per Federal Regulations and/or the qualifying Institutional Review Board (IRB) or Ethics Committee (EC). A blank copy of the IRB/EC-approved form must be kept on-site site and by the sponsor. The signed original for each subject must be kept in the subjects will be given a copy of their signed informed consent.

7.0 Administrative Study Information

7.1 Pre-Study Site Visits (Qualification and Site Initiation Visits)

The Sponsor will confirm the site's ability to perform the study, store study equipment, and recruit patients. This is typically done during a visit to the site to meet with the Investigator(s), but may be done remotely in certain circumstances.

7.2 Investigator Records and Reports

Where required by applicable regulatory requirements, an investigator signatory will be obtained for the acceptance of the clinical study report. The Investigator(s) will be provided reasonable access to statistical results and tables and will be provided a summary of the study results.

PROTOCOL TITLE

Evaluation of Oscillation and Lung Expansion (OLE) using The Volara® System for treatment of respiratory complications in patients with neuromuscular disease in the home setting

Final Protocol

Protocol Number: CR-RR-2020-005

Date: 11May2022

7.3 Interim Monitoring and Closeout Visit(s)

In-person and/or remote interim monitoring and close-out visits may be conducted by the Sponsor for quality assurance.

7.4 Materials Provided by the Sponsor

The Sponsor will supply The Volara® System devices (as required) and as agreed upon in the study agreement.

8.0 Changes Necessary after Study Initiation

If there are changes to the study plan or protocol, these changes will be agreed upon by the Sponsor, its acting representative (if appropriate), the Investigator(s), and the IRB/EC before the changes are implemented. All changes must be documented.

9.0 Study Completion

See section 3.3 for study visit details. Upon completion of the study, a study exit form will be completed for each patient.

12.0 List of Abbreviations

| | |
|------|--|
| ADE | Adverse Device Effect |
| BMI | Body Mass Index |
| CHFO | Continuous High Frequency Oscillation |
| CPEP | Continuous Positive Expiratory Pressure |
| EC | Ethics Committee |
| ED | Emergency Department |
| GCP | Good Clinical Practice |
| IRB | Institutional Review Board |
| IV | Intravenous |
| MIP | Maximal Inspiratory Pressure |
| NMD | Neuromuscular Disease |
| OLE | Oscillation and Lung Expansion |
| PCF | Peak Cough Flow |
| QOL | Quality of Life |
| SpO2 | Oxygen Saturation – obtained by pulse oximetry |
| SVC | Slow Vital Capacity |
| VC | Vital Capacity |

## Statistical Analysis Plan: CR-RR-2020-005

Study Title:	Evaluation of Oscillation and Lung Expansion (OLE) using The Volara® System for treatment of respiratory complications in patients with neuromuscular disease in the home setting
Study Number:	CR-RR-2020-005
Study Phase:	Post Market
Study Design	The study is a multi-center, non-randomized, open-label, decentralized pilot study using an observational design comparing a retrospective control period to an active treatment period to evaluate the impact of Oscillation and Lung Expansion (OLE) to treat respiratory complications in 70 patients with neuromuscular disease in the home setting. The study will be conducted at 6 to 10 sites in the United States.
Product Name:	The Volara® System
Indication:	The Volara® System is an FDA 510k cleared device (k192143), powered by an internal blower, that delivers oscillation and lung expansion (OLE) therapy using both continuous high-frequency oscillation (CHFO) and continuous positive expiratory pressure (CPEP). The therapy is indicated for mobilization of secretions, lung expansion therapy and the treatment and prevention of pulmonary atelectasis. The device can also provide

STUDY NUMBER: CR-RR-2020-005

PLAN VERSION: 2.0

PLAN VERSION DATE: 28 MAY 2024

[figure not shown]
supplemental oxygen when used with  
an oxygen supply.

**LIST OF ABBREVIATIONS AND DEFINITIONS OF TERMS**

AE	adverse event
ATS	American Thoracic Society
BMI	body mass index
CI	confidence interval
eCRF	electronic case report form
ED	emergency department
FAS	full analysis set
FDA	Food and Drug Administration
ICF	informed consent form
ICU	intensive care unit
ID	identification
IV	intravenous
MedDRA	Medical Dictionary for Regulatory Activities
MIP	maximal inspiratory pressure
N	sample size
NMD	neuromuscular disease
OLE	oscillation and lung expansion
PCF	peak cough flow
PPS	per protocol set
PT	preferred term
QOL	quality of life
SAE	serious adverse event
SAP	statistical analysis plan
SAS	Statistical Analysis Software
SD	standard deviation

STUDY NUMBER: CR-RR-2020-005 | PLAN VERSION: 2.0 | PLAN VERSION DATE: 28 MAY 2024

SOC	system organ class
SPO2	oxygen saturation
SRI	severe respiratory insufficiency
SS	safety analysis set
SVC	slow vital capacity
US	United States
WHO	World Health Organization

## 1. STUDY DETAILS

This statistical analysis plan (SAP) is provided to describe the framework for the reporting, summarization, and statistical analysis methodology of the safety and efficacy parameters measured throughout the study. It is based on clinical trial protocol CR-RR-2020-005 Revision D, dated 11 MAY 2022.

### 1.1 Study Objectives and Endpoints

The objective of the study is the evaluation of the impact of Oscillation and Lung Expansion (OLE) therapy to treat respiratory complications of neuromuscular disease in patients.

Primary Endpoint:

- Frequency of exacerbations of pulmonary disease requiring medical intervention (e. g. one or more of the following):
  - Hospitalization
  - Emergency Department (ED) Visit
  - Unscheduled Antibiotics for Respiratory Infection
  - Unscheduled outpatient visit

Secondary Endpoints:

- Pulmonary function tests
  - Slow Vital Capacity (SVC)
  - Peak Cough Flow (PCF)
  - Resting Oxygen Saturation (SPO2)
  - Maximal Inspiratory Pressure (MIP)
- Number of hospital admissions
- Total hospital length of stay
- Number of intensive care unit (ICU) admissions

- Total ICU length of stay
- Number of outpatient visits for pulmonary complication (Unscheduled Physician's office, Urgent Care Visits, ED visits)
- Number of antibiotic use days during episodes of pulmonary exacerbation
  - IV (intravenous) antibiotic days
  - Oral antibiotic days
  - Nebulized antibiotic days
- Quality of Life (QOL) Assessment
- Patient/caregiver satisfaction with therapy

## 1.2 Study Design

### 1.2.1 Overall Study Design and Plan

The study will be a multi-center, non-randomized, open-label, pilot study. It is a decentralized study using an observational design comparing a retrospective control period to an active treatment period. Approximately 70 patients will be enrolled from identified clinics that currently treat neuromuscular disease (NMD) patients. All enrolled subjects will receive Oscillation and Lung Expansion (OLE) treatment during the active treatment period. Subjects will be recruited from 6 to 10 sites in the United States (US).

Study subjects will serve as their own control. Medical records will be reviewed for each study subject for the 12-month period prior to initiation of OLE therapy. The study will display the frequency of exacerbations experienced prior to treatment with OLE and the frequency of exacerbations experienced in the active treatment period, during which study subjects receive treatment with The Volara® System. In addition, specific healthcare utilization indicators including hospitalizations, antibiotic use, and ED visits for pulmonary complications will be documented for each study period.

Pulmonary function measures, a quality of life (QOL) assessment and a satisfaction survey will be assessed at baseline and during the active treatment period.

### **1.2.2 Determination of Sample Size**

A total of approximately 70 subjects will be enrolled. The sample size for this study is a convenience sample. This is a descriptive study with no formal hypothesis testing.

### **1.2.3 Blinding**

The study is open label and will not have blinding of any investigational products.

### **1.2.4 Schedule of Visits and Procedures**

All study subjects will complete a virtual home baseline study visit for initiation of the trial and enrollment into the study. Following the baseline visit, each study subject will complete 3 follow-up visits. The first follow-up visit will be approximately 1 month after initiating therapy and will occur virtually or by phone. Follow-up visits 2 and 3 will be done virtually and will occur approximately 3 months and 6 months after initiation of OLE therapy. Pulmonary function measures will be collected at baseline and at the end of each month of therapy during the active treatment period.

## **1.3 Analysis Populations**

Three main analysis sets are defined for this study.

### **1.3.1 Definition of Analysis Populations**

*Full analysis set (FAS):* all patients who have at least 1 exacerbation event requiring medical intervention in the 12-month pre-treatment historical control period and who received at least one Volara® treatment.

*Per protocol set (PPS):* all patients in the FAS who do not have any protocol deviations that could impact the primary endpoint.

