3.0 Study Design**3.1 Overview of Study Design****3.1.1 Design:**

The study will be a non-randomized open label pilot study. It is a decentralized study using an observational design comparing a retrospective control period to an active treatment period. Approximately seventy (70) patients will be enrolled from identified clinics that currently treat NMD patients. All enrolled subjects will receive OLE treatment during the active treatment period. Subjects will be recruited from six to ten (6-10) sites in the US.

Study subjects will serve as their own control. Medical records will be reviewed for each study subject for the twelve-month period prior to initiation of OLE therapy. The study will compare the frequency of exacerbations experienced prior to treatment with OLE to the frequency of exacerbations experienced in the active treatment period, during which study subjects receive treatment with The Volara® System. In addition, specific healthcare utilization indicators including

PROTOCOL TITLE

Evaluation of Oscillation and Lung Expansion (OLE) using The Volara® System for treatment of respiratory complications in patients with neuromuscular disease in the home setting

Final Protocol

Protocol Number: CR-RR-2020-005**Date:** 11May2022

hospitalizations, antibiotic use, and emergency department (ED) visits for pulmonary complications will be documented for each study period.

Pulmonary function measures, a quality of life (QOL) assessment and a satisfaction survey will be assessed at baseline and compared to results collected during the active treatment period. Adherence to OLE therapy will be collected throughout the active treatment period.

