#### Deviations that should not lead to exclusion of data in a PP analysis

- Patients who violate inclusion/exclusion criteria relating to patient safety
- Issues with documentation of informed consent
- Issues with SAE reporting

Safety analysis set (SS): the set of all patients who have received OLE therapy with The Volara® System.

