## 2.4 Endpoint Analyses

### 2.4.1 Primary Endpoint

The primary endpoint analysis will be carried out on the FAS with a supportive analysis performed on the PPS.

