#### 2.4.2 Secondary Endpoints

All secondary endpoint analyses will be performed on the FAS.

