16.2.6.1	FAS	Exacerbations of Pulmonary Disease Requiring Medical Intervention
16.2.6.2	FAS	Pulmonary Function Tests
16.2.6.3	FAS	Medical Interventions for Exacerbations of Pulmonary Disease
16.2.6.4.1	FAS	Quality of Life Assessment - Respiratory Complaints Overall Score
16.2.6.4.2	FAS	Quality of Life Assessment - Respiratory Complaints
16.2.6.5	FAS	Patient/caregiver Satisfaction with Prior Therapy and The Volara® System
16.2.7.1.1	SS	Pre-Treatment Adverse Events
16.2.7.1.2	SS	Treatment Emergent Adverse Events
16.2.7.1.3	SS	Serious Pre-Treatment Adverse Events

STUDY NUMBER: CR-RR-2020-005

PLAN VERSION: 2.0

PLAN VERSION DATE: 28 MAY 2024

16.2.7.1.4	SS	Serious Treatment Emergent Adverse Events
16.2.7.1.5	SS	Treatment Emergent Adverse Events Related to Study Device
16.2.7.1.6	SS	Serious Treatment Emergent Adverse Events Related to Study Device
16.2.7.1.7	SS	Treatment Emergent Adverse Events Leading to Discontinuation
16.2.7.1.8	SS	Treatment Emergent Adverse Events Leading to Death

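### The SAP's full analysis set requires an exacerbation in the control period, so any treated patient it removes could only have reduced an observed mean fall; the number removed is probably small and may be zero

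*SAP*

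**What the plan says.** SAP 1.3.1 sets two conditions for the FAS. The first concerns history: "all patients who have at least 1 exacerbation event requiring medical intervention in the 12-month pre-treatment historical control period". The second concerns exposure: "and who received at least one Volara® treatment". The per protocol set (PPS) is nested inside it: "all patients in the FAS who do not have any protocol deviations that could impact the primary endpoint".

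The efficacy analyses follow from these two sets. SAP 2.4.1: "The primary endpoint analysis will be carried out on the FAS with a supportive analysis performed on the PPS". SAP 2.4.2: "All secondary endpoint analyses will be performed on the FAS". In SAP Appendix 1 every efficacy table (14.2.1.1 to 14.2.5.2) is labelled FAS or PPS. Every efficacy listing (16.2.6.1 to 16.2.6.5) is labelled FAS, including Listing 16.2.6.1, "Exacerbations of Pulmonary Disease Requiring Medical Intervention". The only set that holds everyone treated is the safety set, "the set of all patients who have received OLE therapy with The Volara® System", and SAP 2.5 assigns it to safety.

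Protocol 3.1.1 describes the comparison, counted back from the start of OLE, without a filter on what the chart shows: "Study subjects will serve as their own control. Medical records will be reviewed for each study subject for the twelve-month period prior to initiation of" (the quote stops before the therapy is named). Protocol 3.2.1 requires, at entry, at least one respiratory exacerbation in 6 months or at least two in 12.

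**The concern.** The primary result is a mean within-patient difference in exacerbation counts with a 95% confidence interval, in a single-arm, open-label study. The control-period count is one of the two terms of that difference. A set that admits a treated patient only if the control period holds an event is selected on part of its own outcome. The selection works in one direction, because it can remove patients with a control count of zero but never patients with a high one.

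The supportive PPS analysis cannot reveal the effect, since it is drawn from the same set. SAP 2.4.1.2 says that all exacerbations in both periods will be listed, but the listing is restricted to the FAS. Exacerbations on treatment in removed patients would therefore appear in no efficacy output.

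**Working it through.** The plan gives no figure to reproduce: about 70 patients is a convenience sample (SAP 1.2.2), with no assumed effect or variability. The check is in four steps.

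**1. Bound on each removed patient.** SAP 2.4.1.1 defines the difference as D = (active-period count) - (count in the 6 months before treatment start). No event in 12 months implies none in the last 6. So D = active count - 0, which is 0 or more.

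**2. Direction.** Let N be the number treated, k the number removed, d the FAS mean difference, and m the mean active count of those removed.

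mean(all treated) = [(N - k) × d + k × m] / N

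mean(all treated) - d = (k / N) × (m - d)

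Since m is at least 0, this shift is above 0 whenever k > 0 and d < 0. With an observed fall, the FAS always overstates it. With k = 0 nothing changes. If the FAS shows a rise, the direction is not fixed.

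**3. Size under assumptions.** N = 70 is the planned enrolment, taken as the number treated. The values d = -0.50, k and m are assumptions; none is in the documents. For example, k = 3 and m = 0.5 gives (67 × -0.50 + 3 × 0.5) / 70 = -32.0 / 70 = -0.457.

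| k | m = 0 | m = 0.5 | m = 1.0 |
|---|---|---|---|
| 0 | -0.500 | -0.500 | -0.500 |
| 1 | -0.493 | -0.486 | -0.479 |
| 3 | -0.479 | -0.457 | -0.436 |
| 7 | -0.450 | -0.400 | -0.350 |

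**4. Who could be removed.** The entry rule is stricter than the FAS rule, so a patient who meets it on the same records, definition and window is never removed. A gamma-Poisson simulation with no treatment effect (assumed mean 0.5 to 1.5 events per 6 months, shape 1 or 2, 2,000,000 patients per setting) found no such patient in any setting. The possible routes are these:

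- *History accepted but not in the chart as an endpoint event.* Eligibility is assessed at the virtual baseline visit (Protocol 3.3.3.1), while Protocol 3.3.3.2 describes obtaining records for enrolled subjects. Entry asks for an exacerbation with unplanned intervention. The endpoint (Protocol 3.3.4.1, SAP 2.4.1.1) also needs documented infection, x-ray change or changed respiratory support. An entry event need not be an endpoint event.
- *Enrolled against the criterion.* The Protocol Synopsis makes removal of such subjects possible, not mandatory.
- *Window moved by the 2 to 4 week run-in (Protocol 3.3.3.4).* This requires no event in the 6 months before entry and all qualifying events in the oldest weeks of the look-back. In the simulation at most about 12% of eligible patients had events only in months 7 to 12. With two events spread independently over 26 weeks, 0.12 × (4/26)² = 0.0028, or about 0.2 of 70 patients. This route is nearly empty.

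**The case against.** The strongest objection is that entry already demands more than the FAS does, so the filter may remove nobody. That stands as a limit on size. The documents do not ensure that entry is verified on the same records and definition, so it does not show that k is zero.

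A second objection concerns missing records. If a patient's history was accepted but the records were never obtained, the control count is unknown. Scoring it as 0 would create artificial no-change or worsening, and SAP 2.6.1 rules out imputation. This stands, and the fix must separate a reviewed chart with no event from an absent chart.

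Third, the exclusion is partly visible: SAP 2.2 reports the numbers treated and in the FAS, and the safety tables keep these patients. That shows a headcount, not their exacerbations. Protocol 5.0 makes device-related effects and device complaints reportable, so an exacerbation judged unrelated need not appear among safety events.

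A reader might also infer several stronger points that the documents do not support:

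- *That everyone who can only stay level or worsen is dropped.* Patients with events only in months 7 to 12 stay in with a 6-month count of 0 (about 9% to 12% of eligible patients in the simulation).
- *That dropped patients could not improve on anything.* The bound holds for the exacerbation count and, in effect, for utilisation tied to it. On lung function, quality of life or satisfaction they could improve.
- *That the SAP contradicts the protocol.* The protocol defines no analysis sets, and Protocol 3.5.2 leaves the analysis detail and subsets to the SAP. The filter's absence from SAP section 3 is therefore a weak point.

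**Conclusion.** The concern holds in direction, and its size is unknown. The FAS rule conditions the primary analysis set on the baseline half of the paired outcome. If it removes any treated patient and the FAS shows a fall, that fall is overstated. This follows from the definitions alone.

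The number removed is probably small and may be zero. On the illustrative assumptions, removing 3 of 70 with a mean active count of 0.5 to 1.0 means that a FAS mean of -0.50 stands in for -0.46 to -0.44. Larger distortions in the table need larger assumed k and m, and should not be read as estimates.

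Regression to the mean from the entry criterion is a separate and probably larger problem. In the same no-effect simulation, meeting the entry rule alone produced a mean difference of -0.245 to -0.547. Changing the analysis set does not remove that. The change is still worth making, because it removes an avoidable one-sided selection and alters no result if k is zero.

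**What to change.** - Define the FAS as all patients who received at least one Volara treatment and whose control-period records were obtained and reviewed. Count a reviewed chart with no qualifying event as 0. Treat unobtained records as missing, not as 0, and report how many there are.
- Keep the present definition as a supportive, chart-confirmed set, and repeat the primary table on it.
- Report how many treated patients the chart-confirmed set removes, with their active-period exacerbation counts.
- Make Listing 16.2.6.1 cover all treated patients.

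The cost is SAP wording and programming. The FAS tables and listings in Appendix 1 are run on the wider set, the PPS follows because it is nested in the FAS, and the primary table has one further run. No new data are collected. The downside for the sponsor is that the headline difference may be slightly less favourable.
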